8.2.5.2 Statistical Methods for Safety Analyses

Safety and tolerability will be assessed by clinical review of all relevant parameters including AEs, laboratory tests, and vital signs. Safety summaries will be pooled across all indications.

Immune related adverse experiences are prespecified as events of interest. These events will be summarized in separate tables from other AEs by toxicity grade and will include the counts, percentage, and 95% CI. Any AE of unknown etiology associated with pembrolizumab exposure will be evaluated to determine if it is possibly an ECI of a potentially immunologic etiology (irECI). Other ECIs listed in Section 7.2.3.2 will also be summarized in the same manner as irAEs.

Adverse experiences (specific terms as well as system organ class terms) and predefined limits of change in laboratory, and vital sign parameters that are not pre-specified as events of interest will be summarized with descriptive statistics (counts, percentage, mean, standard deviation, etc.).

Continuous measures such as changes from baseline in laboratory, and vital signs parameters that are not pre-specified as events of interest will be summarized using descriptive statistics (mean, standard deviation, etc.) for baseline, on-treatment, and change from baseline values.

8.2.5.3 Summaries of Baseline Characteristics, Demographics, and Other Analyses

8.2.5.3.1 Demographic and Baseline Characteristics

Baseline characteristics will be assessed by the use of tables and/or graphs for each indication. No statistical hypothesis tests will be performed on these characteristics. The number and percentage of subjects screened, allocated, the primary reasons for screening failure, and the primary reason for discontinuation will be displayed. Demographic variables (e.g., age, gender), baseline characteristics, primary and secondary diagnoses, and prior and concomitant therapies will be summarized by treatment either by descriptive statistics or categorical tables.

8.2.6 Multiplicity

The false positive rate for testing the primary efficacy endpoint in each disease indication is controlled at 0.08 (1-sided) for each cohort. No additional multiplicity adjustment is required because each disease indication will be evaluated independently.

8.2.7 Sample Size and Power Calculations

Efficacy

Within each indication, the study will enroll a minimum of 6 subjects. Following the time that at least 6 subjects have had at least 1 post-baseline response assessment, a sequential monitoring procedure will be used to evaluate for efficacy and futility simultaneously based on the number of subjects with a confirmed or unconfirmed response according to the rules outlined in [Figure 2](#), [Table 11](#), and [Table 12](#).

Enrollment will not be suspended at 6 subjects for the initial evaluation of efficacy.

Once at least 6 subjects are evaluable for confirmed or unconfirmed response, subsequent rules for pausing enrollment and future evaluations will be based on the boundaries identified by the sequential monitoring procedure. If 0 out of the first 6 subjects with a post-baseline evaluation have a confirmed or unconfirmed response following the first post-baseline assessment, then enrollment will be paused in that indication. The first 6 subjects and any additional subjects enrolled up to the time that the first 6 subjects are evaluated will continue to be followed for response. If the required number of subjects subsequently develop a confirmed or unconfirmed response to continue enrollment according to [Figure 2](#), [Table 11](#), and [Table 12](#), then enrollment may resume in that indication. If ≥ 1 of the first 6 subjects with a post-baseline evaluation have a confirmed or unconfirmed response, then enrollment

will continue. Depending on the enrollment rate, additional monitoring may be performed according to the boundaries defined in [Figure 2](#), [Table 11](#), and [Table 12](#) until approximately 22 subjects is enrolled within an indication.

If at any time during the trial, the efficacy boundary is crossed for a given indication, enrollment will continue to 22 subjects and subsequent trial planning may be initiated.

If enrollment within an indication is so rapid that 22 subjects are assigned a screening slot for potential enrollment at the time that the first 6 subjects are evaluable for response, then no sequential monitoring will be performed. If enrollment within an indication is so slow that a cohort is unlikely to complete within a reasonable amount of time, a cohort may be closed (e.g. low prevalence of PD-L1 such that fewer than 3 PD-L1 positive subjects are enrolled within a cohort after approximately 6 months of screening activity from all sites).

With an approximate maximum of 22 subjects enrolled within each indication, the study provides 80% power to demonstrate that the best ORR induced by pembrolizumab exceeds 10% at an overall one-sided 8% alpha-level, if the true best ORR is 35%. The null hypothesis of 10% is based on the assumption that the population for each indication is expected to consist of subjects with incurable solid tumors that have failed multiple lines of standard therapy. The best ORR for the limited treatment options available in these subject populations is generally <10%. The alternative best ORR is determined to be a clinically meaningful improvement over other standard treatment options within each studied indication. The calculation is based on the binomialSPRT function in the gsDesign package and is carried out using R assuming a null best ORR of 10%, an alternative best ORR of 35%, type I error of 0.08 and type II error of 0.2 (binomialSPRT (p0=0.1, p1=0.35, alpha=0.08, beta=0.2, minn=6, maxn=22)).

For the final analysis, the response assessment will be based on confirmed best ORR. The adjusted p-value and repeated confidence interval will be computed using sequential methods outlined by Jennison and Turnbull (2000) [33]. The minimum criterion for success is that the lower bound of the adjusted CI > 10%. Given the underlying true rate, this may occur when at least 6/22 subjects develop a confirmed PR or CR. [Table 15](#) summarizes the power under various assumptions.

If the optional exploratory efficacy objective of best ORR per RECIST 1.1 based on central radiology review, best ORR per RANO criteria (GBM cohort), or best ORR per PCWG2 (prostate cancer cohort) is evaluated in an indication, and if fewer than 22 subjects in the respective indication have centrally confirmed measurable disease at baseline in that indication, then additional subjects may be enrolled to ensure that at least 22 subjects with centrally confirmed measurable disease are evaluable for the applicable central radiologist response assessment.

Table 15 Operating Characteristics of the Sequential Monitoring Approach

True Response Rate (RR)	Probability of Stopping for Futility	Probability of Go at end of Study	Average Sample Size
10%	0.92	0.05	9.9
15%	0.76	0.15	12.6
20%	0.57	0.31	15.2
25%	0.39	0.50	17.3
30%	0.25	0.67	18.9
35%	0.14	0.80	20.1
40%	0.08	0.89	20.9
45%	0.04	0.95	21.4
50%	0.02	0.97	21.7

Because the sample size within each indication is 22 subjects (assuming no additional subjects needed for the optional exploratory objective evaluation) the sample size for the entire study is approximately 440 subjects.

Safety

The probability of observing at least 10 subjects with a Grade 3-5 immune related in this study depends on the number of subjects treated and the underlying percentage of subjects with irAEs in the study population. If the underlying incidence of Grade 3-5 irAE is 10%, there is a 77% chance of observing at least 10 subjects with irAEs among the minimum 120 subjects enrolled in the study across all indications, whereas if the underlying incidence is 5% there is a 7.8% chance of observing at 10 occurrences or irAEs. [Table 16](#) provides the point estimate and 95% CI for the underlying percentage of subjects with irAEs given various hypothetical numbers of subjects with irAEs and sample size across indications.

Table 16 Point Estimate and 95% CI for Hypothetical Number of Subjects with a Grade 3-5 irAE

Number of Subjects with Grade 3-5 irAE	Number of Subjects	Point Estimate	95% CI†
10	120	8.3%	(4.1%, 14.8%)
15	120	12.5%	(7.2%, 19.8%)
20	120	16.7%	(10.5%, 24.6%)
10	220	4.5%	(2.2%, 8.2%)
15	220	6.8%	(3.9%, 11.0%)
20	220	9.1%	(5.6%, 13.7%)
10	320	3.1%	(1.5%, 5.7%)
15	320	4.7%	(2.6%, 7.6%)
20	320	6.3%	(3.9%, 9.5%)
10	440	2.3%	(1.1%, 4.1%)
15	440	3.4%	(1.9%, 5.6%)
20	440	4.5%	(2.8%, 6.9%)
† Based on the 2-tailed exact confidence interval of a binomial proportion (Clopper and Pearson, 1934) [34].			

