8.1.3 Power and Sample Size

Within each indication, the study will enroll a minimum of 6 subjects. Following the time that at least 6 subjects have had at least 1 post-baseline response assessment, a sequential monitoring procedure will be used to evaluate for efficacy and futility simultaneously based on the number of subjects with a confirmed or unconfirmed response according to the rules outlined in [Figure 2](#), [Table 11](#), and [Table 12](#).

Depending on the enrollment rate, it is possible that more than 6 subjects may be enrolled prior to the first evaluation of efficacy or futility. Enrollment is expected to be continuous and will not be held within an indication.

Once at least 6 subjects are evaluable for confirmed or unconfirmed response, subsequent rules for pausing enrollment and future evaluations will be based on the boundaries identified by the sequential monitoring procedure. Approximately 22 subjects will be enrolled in each indication. The total sample size is approximately 440 subjects. Further details are provided in Section 8.2.7.

With 22 subjects per indication, this study provides 80% power to demonstrate that the best ORR induced by pembrolizumab exceeds 10% at an overall one-sided 8% alpha-level, if the true best ORR within an indication is 35%. The underlying treatment effect is regarded as clinically important in each of the indications studied. The calculation is based on the

binomialSPRT function in the gsDesign package and is carried out using R. The minimum criterion for success is that the lower bound of the repeated CI > 10% [33]. Given the underlying true rate, this may occur when at least 6/22 subjects develop a response. Further details are provided in Section 8.2.7.

[figure not shown]

Figure 2 Sequential Monitoring Rules for Efficacy and Futility

Table 11 Decision Rules Based on Efficacy Bounds

Monitoring Point (# Subjects)	Minimum # Responders to Start Future Study Planning
6-7	3
8-12	4
13-17	5
18-22*	6
23-26	7
27-30	8
Design assumes overall Type I error of 8% (1-sided) and 80% power. *Success at the final analysis requires $\geq 6/22$ subjects with a response.	

Table 12 Decision Rules Based on Futility Bounds

Monitoring Point (# Subjects)	Maximum # Subjects with Response to Declare Futility
6-9	0
10-14	1
15-19	2
20-24*	3
25-28	4
29-30	5
Design assumes overall Type I error of 8% (1-sided) and 80% power. *Success at the final analysis requires $\geq 6/22$ subjects with a response.	

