8.1.4 Interim Analysis

Multiple interim analyses may be performed in this study due to the sequential design of the trial. Results will be reviewed by the study team. The endpoint(s), timing, and purpose of the interim analysis are summarized in the [Table 13](#). The decision rule and other statistical details are further described in Section 8.2.9.

Table 13 Summary of Interim Analysis Strategy

Key Endpoints for Interim Analysis	Timing of Interim Analysis	Purpose of Interim Analysis
Objective response rate (confirmed or unconfirmed)	Sequential monitoring approach	
• Stop for futility• Go to future study planning

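### Table 15's Go column is presented as power, but it exceeds the largest value the 6/22 success rule can reach; it matches the probability of crossing the Table 11 planning boundary

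*Combined protocol and SAP*

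**What the plan says.** **Success rule.** In 8.2.7 the minimum criterion is that the lower limit of the adjusted confidence interval exceeds 10%, and "this may occur when at least 6/22 subjects develop a confirmed PR or CR". The footnotes to Tables 11 and 12 (8.1.3) are firmer: "Success at the final analysis requires" at least 6 of 22 responders.

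**Power.** In 8.2.7, "the study provides 80% power to demonstrate that the best ORR induced by pembrolizumab exceeds 10% at an overall one-sided 8% alpha-level", for a true rate of 35%; 8.1.3 repeats the claim. Straight after the 6/22 rule, 8.2.7 says Table 15 "summarizes the power under various assumptions". The column in question is headed "Probability of Go at end of Study" and is not defined.

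**Planning boundary.** Table 11 is headed "Minimum # Responders to Start Future Study Planning", and Table 13 (8.1.4) gives one purpose of the interim looks as "Go to future study planning". Crossing does not end a cohort: 8.2.7 has enrolment continue to 22. Interim looks may count unconfirmed responses (8.2.5.1, 8.2.9); the final analysis counts only confirmed ones.

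**The concern.** The plan makes two separate decisions per cohort: whether to begin planning a further study (Table 11, at any look) and whether the cohort succeeded (6/22 confirmed, at the end). Table 15 is the plan's only display of efficacy operating characteristics, and it serves 20 cohort decisions. If its Go column describes the first decision while its header and the text assign it to the second, a reader will take false success at a true 10% to be about three times what it can be, and will overstate success at 15 to 25%, where weak signals are judged.

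**Working it through.** **Inputs.** Null 10%, alternative 35%, alpha 0.08, beta 0.20, first look at 6, maximum 22 (8.2.7). Table 11 minimum responders: 3 at n = 6–7, 4 at 8–12, 5 at 13–17, 6 at 18–22. Table 12 futility maximum: 0 at 6–9, 1 at 10–14, 2 at 15–19, 3 at 20–24.

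**Step 1: reproduce the boundaries.** The sequential probability ratio test lines are

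- upper: ceil{[ln(0.8/0.08) + n·ln(0.9/0.65)] / ln[(0.35×0.9)/(0.1×0.65)]} = ceil[(2.3026 + 0.3254n)/1.5782]
- lower: floor{[ln(0.2/0.92) + n·ln(0.9/0.65)] / 1.5782} = floor[(−1.5261 + 0.3254n)/1.5782]

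At n = 22 the upper line is 5.995, hence 6. The two formulas reproduce every row of Tables 11 and 12 for n = 6 to 30. So 8% and 80% are the inputs that generate the lines.

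**Step 2: ceiling for the success rule.** Success needs 6 or more confirmed responses among 22. No look schedule, futility rule, response delay or confirmation requirement can raise its probability above P(X ≥ 6 | 22, p).

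**Step 3: candidate readings of the Go column.** Exact recursion over binomial paths, one subject at a time, with looks at n = 6 to 21:

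| True rate | Printed Go | ≥6/22, no monitoring | ≥6/22, futility after every subject | Cross Table 11 at 6–21 |
|---|---|---|---|---|
| 10% | 0.05 | 0.018 | 0.015 | 0.046 |
| 15% | 0.15 | 0.100 | 0.085 | 0.151 |
| 20% | 0.31 | 0.267 | 0.231 | 0.314 |
| 25% | 0.50 | 0.483 | 0.428 | 0.500 |
| 30% | 0.67 | 0.687 | 0.622 | 0.671 |
| 35% | 0.80 | 0.837 | 0.777 | 0.803 |
| 40% | 0.89 | 0.928 | 0.881 | 0.891 |
| 45% | 0.95 | 0.973 | 0.941 | 0.944 |
| 50% | 0.97 | 0.992 | 0.972 | 0.973 |

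- Printed minus ceiling: +3.2, +5.0, +4.3 and +1.7 points at 10, 15, 20 and 25%. Two-decimal rounding allows 0.5.
- Printed minus the value with futility after every subject: +3.5, +6.5, +7.9, +7.2, +4.8 and +2.3 points at 10 to 35%.
- Crossing at 6–21 matches 8 of 9 printed values, largest gap 0.006 (at 45%). Crossing at 6–22 matches 3 of 9 (largest gap 0.016), ≥6/22 with futility 1 of 9 (0.079), and ≥6/22 without monitoring 0 of 9 (0.050).

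**Step 4: the other Table 15 columns.** With futility stops at 6–21, average sample size runs from 9.91 to 21.67 (within 0.07 of the printed values). Futility probability is 0.915, 0.758, 0.565, 0.385, 0.244, 0.145, 0.082, 0.045 and 0.023 (within 0.007).

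**Step 5: how often the two decisions disagree.** With looks after every subject, the probability of crossing at 6–21 but not finishing with 6/22, as a share of crossings:

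- 10%: 0.0324 / 0.0465 = 70%
- 25%: 0.0877 / 0.500 = 18%
- 35%: 0.0374 / 0.803 = 5%

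The share is the same whether or not futility is suspended after crossing. At 10%, for example, 0.0266 reach 22 and miss and 0.0058 stop for futility (sum 0.0324); with futility suspended, all 0.0324 reach 22 and miss.

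**Step 6: other look schedules for ≥6/22** (type I error at 10% / power at 35%). Futility looks at 6, 12 and 18: 1.6% / 79.4%. A look at 6 only: 1.6% / 79.9%.

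**The case against.** **This is only a label.** Table 15's title refers to the sequential monitoring approach, and Table 13 uses Go for planning. That supports the boundary-crossing reading. It does not remove the conflict: the header places the decision at the end of the study, and the text calls the table power directly after stating the 6/22 rule.

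**The attribution is not proved.** The documents do not say how the column was computed, and the cut at subject 21 is chosen by fit. The futility column fits less tightly: the version above misses the printed two-decimal value at 10, 30 and 35%, and protecting crossed cohorts from futility, as 8.2.7 implies, widens the largest gap to 0.011 (0.909 against 0.92). This stands, so the relabelling should wait for a check of the sponsor's code. The ceiling in step 2 does not depend on it.

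**Cohorts may exceed 22.** The plan says approximately 22 and allows additions. The 83.7% maximum therefore holds only for exactly 22 subjects: with Table 11's thresholds and no stopping, power at 35% is P(X ≥ 7 | 26) = 85.8% and P(X ≥ 8 | 30) = 87.6%. This does not rescue the column. At 10%, P(X ≥ 7 | 26) is 0.012, further below 0.05.

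**The error is cautious and 80% is roughly right.** Overstating false success is the safer direction, and 80% at 35% lies within the attainable range. Both are true and limit the severity. At 15 to 25%, however, the column also exceeds anything the success rule can deliver.

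**Conclusion.** The point holds. As the probability of at least 6/22, the Go column is impossible at true rates of 10 to 25%; that is an inequality for 22-subject cohorts and needs no assumption about monitoring. That it shows crossing of Table 11 before subject 22 is a strong inference, not a documented fact.

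For the 6/22 rule, type I error and power are 1.5% / 77.7% with futility after every subject and 1.8% / 83.7% with no monitoring. These assume exactly 22 subjects in cohorts that complete, every response confirmed and visible at each look, and permanent futility stops. The second pair is a true upper bound; 77.7% is not a floor. As an illustration with assumed values, if 80% or 60% of responders show at the first scan and the rest four subjects later, power at 35% with looks after every subject falls to 73.5% or 68.0%.

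The 8% limit is not breached and the false-positive rate is conservative. The fault lies in the stated operating characteristics, so this should be fixed but does not threaten the design.

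**What to change.** 1. Check the sponsor's code, define Go in Table 15 and, if the code confirms it, relabel the column: *Probability of crossing the Table 11 boundary before subject 22 (start of further study planning)*.
2. Add a column, *Probability of at least 6/22 confirmed responses at the final analysis*, giving the two ≥6/22 series tabulated above (futility after every subject; no monitoring). Mark it as assuming 22-subject cohorts, every response confirmed and visible at each look, and permanent futility stops. Point the power sentence in 8.2.7 to this column.
3. In 8.1.3 and 8.2.7, state that 8% and 80% are nominal design inputs; that under the marked assumptions type I error at 10% and power at 35% run from 1.5% and 77.7% to 1.8% and 83.7%; that responses appearing after an early look can lower power further; that resuming a paused cohort can raise it, to at most 83.7% at 22 subjects; and that 10% and 35% are confirmed response rates.

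The cost is one relabelled column, one added column and a short statement in two sections. The single 80% figure becomes a range with stated assumptions. Boundaries, threshold, sample size and conduct do not change.

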8.2.8 Subgroup Analyses and Effect of Baseline Factors

No subgroup analysis is planned.

8.2.9 Interim Analyses

Multiple interim analyses may be performed in this study due to the sequential design of the trial. Results will be reviewed by the study team. The primary best ORR endpoint will be used for all interim decision-making with or without a confirmation assessment; however, a confirmation assessment is required for the final best ORR analyses after 22 subjects are enrolled in a cohort. For purpose of interim monitoring, subjects who are still on study but without a post baseline scan will be excluded from the analyses specified in [Table 14](#). The decision rule and other statistical details are further described in Section 8.2.7.

8.2.10 Compliance (Medication Adherence)

A day within the study will be considered an On-Therapy day if the subject receives the study medication infusion. The number of Days Should be on Therapy is the total number of days from the first day of study medication to the date of the last dose of study medication. For each subject, percent compliance will then be calculated using the following formula:

$$\text{Percent Compliance} = \frac{\text{Number of Days on Therapy}}{\text{Number of Days Should be on Therapy}} \times 100$$

Summary statistics will be provided on percent compliance by treatment group for the FAS population.

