5.2 Trial Treatment(s)

The study drug dose and schedule to be used in this trial are outlined below in [Table 2](#).

Table 2 Trial Treatment

Drug	Dose/Potency	Dose Frequency	Route of Administration	Regimen/ Treatment Period	Use
Pembrolizumab	10 mg/kg	Q2W	IV infusion	Day 1 of each cycle	Experimental
The pembrolizumab dosing interval may be withheld due to toxicity as described in Section 5.2.1.2.					

Trial treatment should begin on the day of randomization or as close as possible to the date on which the subject is allocated/assigned.

All trial treatments will be administered on an out-patient basis.

All products indicated in [Table 2](#) will be provided centrally by the Sponsor or locally by the trial site, subsidiary or designee, depending on local country operational or regulatory requirements.

The investigator shall take responsibility for and shall take all steps to maintain appropriate records and ensure appropriate supply, storage, handling, distribution and usage of trial treatments in accordance with the protocol and any applicable laws and regulations.

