5.2.2 Timing of Dose Administration

Study drug should be administered on Day 1 of each cycle after all procedures/assessments have been completed as detailed on the Trial Flow Chart (Section 6.0). Study drug may be administered up to 3 days before or after the scheduled Day 1 of each cycle due to administrative reasons.

All study drug will be administered on an outpatient basis.

Pembrolizumab will be administered as a 30 minute IV infusion every 2 weeks (treatment cycle intervals may be withheld due to toxicity as described in Section 5.2.1.2). Sites should make every effort to target infusion timing to be as close to 30 minutes as possible. However, given the variability of infusion pumps from site to site, a window of -5 minutes and +10 minutes is permitted (i.e., infusion time is 30 minutes: -5 min/+10 min).

The Pharmacy Manual contains specific instructions for pembrolizumab dose calculation, preparation of the infusion solution, and administration.

Continuing Study Drug Administration After Initial Evidence of Radiologic Disease Progression

Immunotherapeutic agents such as pembrolizumab may produce antitumor effects by potentiating endogenous cancer-specific immune responses. The response patterns seen with such an approach may extend beyond the typical time course of responses seen with cytotoxic agents, and can manifest as a clinical response after an initial increase in tumor burden or even the appearance of new lesions.

If initial radiologic imaging shows PD, tumor assessment should be repeated ≥ 4 weeks later in order to confirm PD with the option of continuing treatment per below while awaiting

radiologic confirmation of progression. If repeat imaging shows a reduction in the tumor burden compared to the initial scan demonstrating PD, treatment may be continued as per treatment calendar. If repeat imaging confirms progressive disease, subjects will be discontinued from study therapy (exception noted in Section 7.1.2.5.1). In determining whether or not the tumor burden has increased or decreased, Investigators should consider all target lesions as well as non-target lesions (please refer to the Procedures Manual).

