5.8.1 Discontinuation of Treatment

A subject must be discontinued from treatment (but may continue to be monitored in the trial) for any of the following reasons:

- The subject or legal representative (such as a parent or legal guardian) withdraws consent for treatment
- Confirmed radiographic disease progression outlined in Section 7.1.2.5.1 (exception if the Sponsor approves treatment continuation).

Note: For unconfirmed radiographic disease progression, please see Section 5.2.2

Note: A subject may be granted an exception to continue on treatment with confirmed radiographic progression if clinically stable or clinically improved, please see Section 7.1.2.5.1

- Unacceptable adverse experiences as described in Section 5.2.1.2 and Section 7.2
- Any progression or recurrence of any malignancy, or any occurrence of another malignancy that requires active treatment
- Intercurrent illness other than another malignancy as noted above that prevents further administration of treatment
- Investigator's decision to withdraw the subject
- A confirmed positive serum pregnancy test
- Noncompliance with trial treatment or procedure requirements
- Recurrent Grade 2 pneumonitis
- The subject is lost to follow-up
- Completed 24 months of treatment with pembrolizumab

Note: 24 months of study medication is calculated from the date of first dose. Subjects who stop pembrolizumab after 24 months may be eligible for up to 1 year of additional study treatment if they progress after stopping study treatment provided they meet the requirements detailed in Section 7.1.5.2.1.

- Discontinuation of treatment may be considered for subjects who have attained a confirmed CR that have been treated for at least at least 24 weeks, receiving at least 2 doses of pembrolizumab beyond the date when the initial CR was declared. Subjects who stop pembrolizumab with SD, PR, or CR, may be eligible for up to 1 year of pembrolizumab if they experience disease progression after stopping pembrolizumab. This retreatment is termed the Second Course Phase (Retreatment) and is described in detail in Section 7.1.5.2.1.
- Administrative reasons

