Tumor Biopsies/Archival Tissue Collection/Correlative Studies Blood													
Archival or Newly Obtained Tissue Collection ^e	X ^s												
Correlative Studies Blood Collection ^e		X ^t				X ^t				X ^t			

- a. Treatment cycles are 2 weeks. Imaging should be performed every 8 weeks initially (56 days \pm 7 days) and after 6 months, imaging assessments should be performed every 12 weeks regardless of any treatment delays (i.e. Screening visit, Cycle 5, Cycle 9, Cycle 13 and then every 6 cycles (12 weeks)).
- b. In subjects who discontinue study therapy without documented disease progression, every effort should be made to continue monitoring their disease status by radiologic imaging^p every 8 weeks (\pm 7 days) in the first 6 months and every 12 weeks (\pm 7 days) after Month 6 until (1) the start of new anti-cancer treatment, (2) documented disease progression, (3) death, or (4) the end of the study, whichever occurs first.
- c. Pre-screening informed consent must be obtained prior to sending an archival sample to the vendor for characterization. Subjects that do not have archival tissue available must sign the main study consent prior to undergoing a newly obtained biopsy.
- d. Written consent must be obtained prior to performing any protocol specific procedure. Results of a test performed prior to the subject signing consent as part of routine clinical management are acceptable in lieu of a screening test if performed within the specified time frame (e.g., within 28 days prior to the first dose of trial treatment). Baseline number will be assigned when the study informed consent is signed.
- e. Leftover samples may be kept for Future Biomedical Research if the subject signs the Future Biomedical Research (FBR) consent.
- f. Prior medications – Record all medications taken 28 days before the first dose of trial treatment. Concomitant medications – Enter new medications started during the trial and 30 days after last dose of trial treatment regardless of when the Safety Follow-up visit occurs.

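### Section 8.2.10 divides infusion days by all calendar days from first to last dose, so on a nominal 14-day schedule a subject with two or more doses and none missed scores about 14% falling to about 7%, not 100%.

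*Combined protocol and SAP*

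**What the plan says.** Section 8.2.10 defines percent compliance as days on therapy divided by the days on which the subject should have been on therapy, times 100.

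- Numerator: "A day within the study will be considered an On-Therapy day if the subject receives the study medication infusion".
- Denominator: "The number of Days Should be on Therapy is the total number of days from the first day of study medication", running to the date of the last dose. The section does not say whether both end days count.
- Use: "Summary statistics will be provided on percent compliance by treatment group for the FAS population".

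Dosing is intermittent. Table 2 in Section 5.2 places the infusion on "Day 1 of each cycle". Section 5.2.2 says "Pembrolizumab will be administered as a 30 minute IV infusion every 2 weeks", and footnote a of the Section 6.1 flow chart says "Treatment cycles are 2 weeks". Section 5.2.2 also gives a window: "Study drug may be administered up to 3 days before or after the scheduled Day 1 of each cycle due to administrative reasons".

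Two other sections touch on compliance or exposure. Section 7.1.1.9 compares the volume infused with the volume prepared for each dose given. Section 8.2.11 counts the cycles in which an infusion was received, without a denominator. Neither measures missed doses or alters the 8.2.10 formula.

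**The concern.** The two parts of the ratio are in different units. The numerator counts infusions, at most one per cycle. The denominator counts every calendar day, including about 13 days per cycle on which no infusion is due. A subject who attends every visit therefore cannot score near 100% once a second dose has been given.

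A constant scale error could be removed by multiplying by 14. This one is not constant: the score falls as treatment lengthens even when no dose is missed. Subjects or cohorts with different treatment durations would show different compliance for reasons unrelated to adherence. At stake is one planned table, which would report fully adherent subjects as roughly 7% to 14% compliant.

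**Working it through.** The plan states no numerical compliance value, so there is none to reproduce. The check applies the formula as written.

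**Inputs.** One infusion per 14 days (Sections 5.2, 5.2.2, 6.1). Window of 3 days either side (5.2.2). FAS entry needs only one dose, plus a baseline scan with measurable disease (8.2.4.1). For maximum first-course duration, Section 5.8.1 says "24 months of study medication is calculated from the date of first dose". Taking 24 months as 730 days gives floor(730/14) + 1 = 53 doses.

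**Formula.** For k doses exactly 14 days apart and none missed, the score is k / (14(k−1) + 1) if both end days count (inclusive), or k / (14(k−1)) if not (exclusive).

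| Doses | Inclusive | Exclusive |
|---|---|---|
| 1 | 1/1 = 100% | 1/0, undefined |
| 2 | 2/15 = 13.3% | 2/14 = 14.3% |
| 5 | 5/57 = 8.8% | 5/56 = 8.9% |
| 13 | 13/169 = 7.7% | 13/168 = 7.7% |
| 53 | 53/729 = 7.3% | 53/728 = 7.3% |

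The limit is 1/14 = 7.1%. On the inclusive count the understatement grows from 15/2 = 7.5-fold at 2 doses to 729/53 = 13.75-fold at 53.

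**Dosing window.** For 2 doses with the second given 3 days early, the interval is 11 days: 2/12 = 16.7% inclusive, 2/11 = 18.2% exclusive. Given 3 days late, it is 17 days: 2/18 = 11.1% or 2/17 = 11.8%. At 53 doses, shifting the last dose by 3 days leaves the value between 7.2% and 7.3%.

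**Holds.** Take 13 infusions with one 84-day gap and the other 11 intervals at 14 days. The span is 11 × 14 + 84 = 238 days, so the inclusive score is 13/239 = 5.4%. The gap contains 84/14 − 1 = 5 cycles not given. Scored by cycles, the same subject has 13/18 = 72.2% if those cycles count as scheduled and 13/13 = 100% if they do not.

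**Second Course.** Sections 5.8.1 and 7.1.5.2.1 allow up to a year of retreatment, and 8.2.10 does not limit the last dose to the first course. With assumed timings of 13 doses, a 364-day gap and 13 more doses, the span is 168 + 364 + 168 = 700 days and the inclusive score is 26/701 = 3.7%.

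**The case against.** The strongest reply is that little depends on this figure. No decision rule in the documents uses it. Section 5.8.1 lists noncompliance as a reason to stop treatment but does not refer to this percentage. Infusions are witnessed and volume-checked, infused cycles are summarised separately, and Section 8.0 lets a change to a non-confirmatory analysis be listed and explained in the clinical study report (CSR). All of this stands, and it limits the impact. It does not make the formula right. Section 8.0 says no separate SAP will be issued for the trial endpoints, Section 8.1 refers to 8.2 for full detail, and 8.2.10 is the only compliance formula given. Correcting it silently in programming would depart from the plan without a record.

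Three stronger readings are tempting, and the documents do not support them.

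- A reader might infer that every subject with two or more doses and none missed falls between 7% and 14%. That needs nominal, uninterrupted 14-day spacing. The window, permitted holds and the Second Course all give values outside that range.
- A reader might infer that the protocol settles how holds should be scored. Section 5.2.1.2 makes the dose resumed after a toxicity hold Day 1 of the next cycle, aligned to the new schedule. It states no new schedule for other allowed interruptions, and it gives no compliance rule for either. Only the need to state a rule follows.
- A reader might infer that the repair needs no further data. Section 8.2.11 supplies the numerator only.

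The formula can also rank subjects wrongly: 2 of 3 infusions scores 2/29 = 6.9%, above 45 of 53 at 45/729 = 6.2%. That pair was chosen to illustrate the effect, and it holds only if missed cycles remain scheduled. It is secondary to the main defect.

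**Conclusion.** The formula is wrong as written for intermittent dosing. Assuming exact 14-day spacing, no interruption and a single course, a subject with two or more doses and none missed scores 13.3% or 14.3% at 2 doses, depending on the day count, and falls to 7.3% at 24 months. The correct value is 100% throughout. Departures from nominal spacing move the score further: about 11% to 18% for 2 doses within the window, and 5.4% in the 84-day example. One-dose subjects score 100% or have no defined value.

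The defect is certain on the text but narrow in effect. It spoils one descriptive FAS summary. The response-rate test, the sequential boundaries, the analysis sets and the sample size are untouched. It should be corrected because the table would mislead as planned and the repair is cheap.

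**What to change.** Redefine percent compliance as 100 × infusions received / infusion cycles scheduled, from first to last dose.

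- Count scheduled cycles, not days divided by 14. Two doses 11 days apart would give 2 / (11/14 + 1) = 112% by days but 2/2 = 100% by cycles.
- Apply the measure to the first course only, or to each course separately, so that the off-treatment gap before the Second Course is excluded.
- State whether cycles skipped under protocol-permitted interruptions count as scheduled. One option consistent with Section 5.2.1.2 is that cycles skipped in a toxicity hold do not count, because the resumed dose starts the next cycle on a new schedule. Toxicity holds would then not lower the measure. This is an analysis convention and changes no treatment rule.

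The cost is one formula and a short statement of scope and of how skipped cycles are counted. Infused cycles are already counted for Extent of Exposure, and scheduled cycles can be derived from dosing dates and the 2-week cycle. A rule that depends on the reason for an interruption needs that reason in the analysis database. Section 5.2.1.2 puts the reason for non-toxicity interruptions in the subject's trial record, and the documents do not confirm that it reaches the database. Under Section 8.0 the change can be listed and explained in the CSR.
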